9.1.3.4. Additional Sensitivity Analyses

Additional sensitivity analyses may be performed by using the randomization stratum recorded in EDC in case of discrepancies between IRT and EDC.

Jazz Pharmaceuticals
 {Statistical Analysis Plan - Protocol #}JZP150-201-02

9.1.4. Subgroup Analyses

Subgroup analyses for groups specified in [Section 7.5](#) will be performed for the primary efficacy estimand using the Full Analysis Set 1, for each of the prespecified subgroups. Subgroup variable by treatment interaction will be estimated for Week 12. Normality assumptions will not be reassessed for subgroups. The corresponding parametric or nonparametric analysis used for the overall sample will be applied to each subgroup. Numeric results for subgroup analyses will be summarized. A forest plot summarizing the treatment difference, 95% CI, and p-value for the interaction term estimated at Week 12 will also be provided by each subgroup.

9.1.5. Supplementary Analyses

- Alternative ICE Strategy: The main analysis for the primary estimand in [Section 9.1.2](#) will be repeated based on the Full Analysis Set 1, using hypothetical approach to address the main ICE of treatment discontinuation. The hypothetical approach assumes that results for participants with the ICE would have followed the same trajectory as participants in the same treatment group who didn't have the ICE. Only the CAPS-5 total score data collected at time points that are at or prior to treatment discontinuation will be included in the analysis. The CAPS-5 total score data collected after any treatment discontinuation will be discarded. Missing data will not be imputed and will be addressed with the same MMRM model described in [Section 9.1.2](#).
- Alternative Analysis Set: The main analysis for the primary estimand will be repeated using the Modified Full Analysis Set and Full Analysis Set 2.

9.2. Secondary Efficacy Estimands, Endpoints and Analyses

9.2.1. Key Secondary Estimands

The attributes of the key secondary efficacy estimands are described in [Section 4.2.2](#).

The Key Secondary Estimand 1 variable CGI-S is a 7-point Likert-type rating scale used to assess the severity of participants' PTSD over the past week by qualified medical personnel (i.e., principal investigator, clinical rater). The responses to this investigator-completed scale range from 1 (Normal, not at all ill) to 7 (Among the most extremely ill participants).

The Key Secondary Estimand 2 variable PGI-S is a 5-point Likert-type rating scale used to assess the severity of PTSD over the past week by study participants. The responses to this participant-completed scale range from 1 (None) to 5 (Very severe).

CGI-S and PGI-S are assessed at Baseline and end of Weeks 1, 4, 8, and 12.

9.2.2. Key Secondary Estimands Main Analysis

The main analysis for the key secondary estimands will be conducted based on the Full Analysis Set 1, using treatment policy to address all ICEs. All CGI-S and PGI-S data collected through Week 12 regardless of ICEs will be used in the analysis, including the CGI-S and PGI-S data collected after an ICE. Using the main ICE of treatment discontinuation as the example, [Table 7](#) describes the detailed data mapping method for CGI-S and PGI-S following treatment discontinuation.

Jazz Pharmaceuticals
 {Statistical Analysis Plan - Protocol #}JZP150-201-02

Table 7. Data mapping for CGI-S and PGI-S following treatment discontinuation for the main analyses.

Intercurrent event	CGI-S and PGI-S data mapping
If participant discontinues both study intervention and the study	CGI-S and PGI-S at E/D visit, any unscheduled visit, or safety follow-up will be mapped to Week 4 and/or Week 12, according to the windowing rule in Section 7.2.3 .
If participant discontinues study intervention prior to Week x but remains in the study (x=1, 4, or 8)	CGI-S and PGI-S scores at E/D visit, any unscheduled visit, the additional efficacy follow-up for Week 4, efficacy follow-up visit for Week 12 or safety follow-up will be mapped to Week 1, 4, 8, or Week 12, according to the windowing rule in Section 7.2.3 .
If participant discontinues study intervention between Week x and Week 12 but remains in the study (x=1, 4, or 8)	CGI-S and PGI-S scores at E/D visit, any unscheduled visit, efficacy follow-up visit for Week 12 or safety follow-up will be mapped to Week 12, according to the windowing rule in Section 7.2.3 .

The CGI-S and PGI-S scores will be considered as continuous variables. A MMRM will be used to analyze the key secondary efficacy endpoints, change in CGI-S and PGI-S from Baseline to Week 12, respectively.

The model will include CGI-S or PGI-S change from Baseline to Week 12 as the dependent variable; randomized treatment group, week (as a discrete factor), treatment group by week interaction, randomization stratum, stratum by week interaction, the CGI-S or PGI-S score at Baseline, and baseline by week interaction, as fixed effects, and week as a repeated effect. An unstructured variance-covariance matrix will be used to model the correlation among repeated measurements. Missing data will not be explicitly imputed and will be handled with the MMRM modeling. Alternative covariance structures will be similar to the methodology specified in [Section 9.1.2](#). Similar summary statistics described in [Section 9.1.2](#) will be provided. Similar SAS codes provided in [Section 9.1.2](#) will be used.

A box plot will be presented for the change in CGI-S and PGI-S from Baseline to end to Week 12 by randomized treatment group, separately. The CGI-S and PGI-S data will also be summarized by time point separately.

A separate SAP will be provided for the anchor-based global assessment to determine CAPS-5's clinically meaningful within-patient change threshold, using CGI-S and PGI-S as anchor scales. This supplemental SAP will present analyses intending to support the analysis of the CGI-S and PGI-S assessment as continuous variables.

9.2.3. Key Secondary Estimands Sensitivity Analyses

Sensitivity analyses similar to [Section 9.1.3](#) will be conducted for the key secondary estimands CGI-S and PGI-S separately.

Jazz Pharmaceuticals
 {Statistical Analysis Plan - Protocol #}JZP150-201-02

9.2.4. Key Secondary Estimands Subgroup Analyses

Subgroup analyses similar to [Section 9.1.4](#) will be conducted for the key secondary estimands CGI-S and PGI-S separately.

9.2.5. Key Secondary Estimands Supplementary Analyses

- Alternative ICE Strategy: The main analysis for the key secondary estimands will be repeated based on the Full Analysis Set 1, using hypothetical approach to address the main ICE of treatment discontinuation. The hypothetical approach assumes that results for participants with the ICE would have followed the same trajectory as participants in the same treatment group who didn't have the ICE. Only the CGI-S or PGI-S collected at time points that are at or prior to treatment discontinuation will be included in the analysis. The CGI-S or PGI-S collected after any treatment discontinuation will be discarded. Missing data will not be imputed and will be addressed with the same MMRM model described in Section 9.2.2.
- Alternative Analysis Set: The main analysis for key secondary estimands will be repeated using the Modified Full Analysis Set and Full Analysis Set 2.

9.2.6. Other Secondary Efficacy Endpoints and Analyses

The analysis for all secondary efficacy endpoints, unless specified otherwise, will be based on the Full Analysis Set 1 with all ICEs addressed by the treatment policy strategy. No sensitivity analysis, subgroup analysis, or supplementary analyses will be considered for any secondary efficacy endpoint. No multiplicity adjustment will be considered for any secondary efficacy endpoint. Missing data will not be explicitly imputed for any secondary efficacy endpoint.

9.2.6.1. Responder Analysis

The responders are defined in 3 ways in [Section 4.2.3](#). Three separate responder analyses will be performed for the CAPS-5 total score, CGI-C, and PGI-S responders. Missing data will not be imputed for responder analysis.

The CGI-C is a 7-point Likert-type rating scale widely used to assess efficacy in clinical drug trials ([Guy 1976](#)). Investigators or trained raters will rate their impression of any change in the severity of the participant's condition since Baseline on a 7-point scale ranging from 1 (very much improved) to 7 (very much worse). Ratings will focus on the participants' change in their ability to function due to PTSD. CGI-C is assessed at end of Weeks 4 and 12. The CGI-C responder analysis will be performed for Week 4 and Week 12 separately.

In each responder analysis, the proportion of participants will be compared between each dose of JZP150 and placebo using the Cochran-Mantel-Haenszel (CMH) test stratified by randomization stratum. The point estimate and continuity corrected Wilson's 95% CI (as modified by Newcombe) for the difference of the proportion will also be provided.

Example SAS Code for obtaining the CMH test p-value, point estimate and 95% CI for the difference in proportion is provide below:

```
PROC FREQ DATA=ANAL;
  TABLES STRATUM*TRT*RESPONDER1/CMH;
  RUN;
```

Jazz Pharmaceuticals
 {Statistical Analysis Plan - Protocol #}JZP150-201-02

```
PROC FREQ DATA=ANAL;
TABLES TRT*RESPONDER1/RISKDIFF(CL=(WILSON(CORRECT)));
RUN;
```

9.2.6.2. CAPS-5 total score change from Baseline to Week 4

The CAPS-5 total score is described in [Section 9.1.1](#). The results for the change in the CAPS-5 total score from Baseline to Week 4 will be presented using the Week 4 contrasts of the MMRM modeling results for the primary endpoint (the CAPS-5 total score from Baseline to Week 12). The modeling details are described in [Section 9.1.2](#).

9.2.6.3. Change in B-IPF and SDS from Baseline to Week 12.

The B-IPF is a 7-item participant-reported questionnaire that assesses PTSD-related psychosocial functional impairment in the past 30 days and is assessed at Baseline and end of Week 12. The B-IPF score is derived from the 7 questions regarding functional impairment. The questions are rated on a 7-point scale from 0 (Not at all), 1 to 5 (Somewhat), to 6 (Very much). The B-IPF total score is calculated by summing individual question scores, dividing by the number of questions and then by 6 and multiplying by 100. The B-IPF total score ranges from 0 to 100.

The SDS is a 5-item participant-reported tool that assesses functional impairment in work/school, social life, and family life in the past week. The SDS score is derived from the 3 questions on disability and impairment. The questions are rated on a 11-point scale from 0 (Not at all), 1-3 (Mildly), 4-6 (Moderately), 7-9 (Markedly), and 10 (Severely). The SDS score ranges from 0 to 30 and is assessed at Baseline and end of Weeks 4 and 12.

The change in the B-IPF score from Baseline to Week 12 will be analyzed using an analysis of covariance (ANCOVA) model. The model will include B-IPF score change from Baseline to Week 12 as the dependent variable and randomized treatment group, randomization stratum, and B-IPF score at Baseline as covariates.

Group comparisons from the ANCOVA model will be based on Type III sum of squares. LS means and SE will be provided for each randomized treatment group. The difference between the LS means along with the SE of the difference, 95% CI and associated p-value corresponding to testing the hypothesis of no difference between the randomized treatment groups will also be provided.

The normality assumption of the ANCOVA model will be examined by residual analysis using the Shapiro-Wilk test ([Shapiro and Wilk 1965](#)). Outliers will be examined and if there is clear evidence of non-normality, a non-parametric ANCOVA with the covariate and response variables replaced by their ranks ([Conover and Iman 1982](#)) will be used. In the event of ties in the baseline or change from baseline, average ranks will be used. The non-parametric ANCOVA will include the rank of the B-IPF score change from baseline to Week 12 as the dependent variable and randomized treatment group, randomization stratum, and the rank for B-IPF score at Baseline as a covariate. P-values will be presented from the rank-based ANCOVA. The estimated median difference between the change in B-IPF score from Baseline to Week 12 between randomized treatment groups and asymptotic 95% CIs will be presented using the Hodges-Lehmann estimator ([Hodges and Lehmann 1962](#)).

The example SAS Code for the ANCOVA model is provided below:

Jazz Pharmaceuticals
 {Statistical Analysis Plan - Protocol #}JZP150-201-02

```
PROC MIXED DATA =ANAL METHOD =TYPE3;
CLASS TRT STRATUM;
MODEL CHG = TRT BASE STRATUM/ DDFM=KR RESIDUAL OUTP=RESIDUAL;
LSMEANS TRT/DIFF CL;
RUN;
```

The example SAS code below evaluates the assumption of normality for the residuals from the above ANCOVA model using the Shapiro Wilk test ([Shapiro and Wilk 1965](#)).

```
PROC UNIVARIATE DATA=RESIDUAL NORMAL;
VAR RESID;
RUN;
```

The example SAS code for the non-parametric ANCOVA model is provided below:

```
PROC RANK DATA =ANAL OUT=RANKED TIES=MEAN;
VAR BASE CHG;
RANKS RBASE RCHG;
RUN;
```

```
PROC MIXED DATA=RANKED METHOD=TYPE3;
CLASS TRT STRATUM;
MODEL RCHG = TRT RBASE STRATUM / DDFM=KR RESIDUAL OUTP=RESIDUAL;
RUN;
```

An estimate of the median difference between treatments for the primary endpoint will be reported using Hodges and Lehmann analysis.

```
PROC NPAR1WAY HL ALPHA=.05 DATA=ANAL;
CLASS TRT;
VAR CHG;
RUN;
```

The change in the SDS score from Baseline to Week 12 will be analyzed using a MMRM model. The model will include randomized treatment group, SDS score at Baseline, week (as a discrete factor), treatment by week interaction, baseline by week interaction, and randomization stratum as fixed effects, and week as a repeated effect. An unstructured variance-covariance matrix will be used to model the correlation among repeated measurements. The modeling detail and SAS code are similar to [Section 9.1.2](#).

The SDS data will also be summarized by time point.

9.2.6.4. Change in PCL-5 from Baseline to Weeks 1, 4, 8, and 12.

The PCL-5 is a 20-item participant-reported questionnaire that assesses the 20 DSM-5 symptoms of PTSD. The PCL-5 score is derived from the 20 questions on PTSD symptoms. The questions are rated on a 5-point scale from 0 (Not at all) to 4 (Extremely). The PCL-5 score ranges from 0 to 80 and is assessed at Baseline and end of Weeks 1, 4, 8, and 12. The PCL-5 past week version is administered at end of Week 1 and the PCL-5 past month version is administered at Baseline and end of Weeks 4, 8, and 12.

The change in participant and clinician-reported symptoms of PTSD as assessed by the PCL-5 score from Baseline to Weeks 1, 4, 8, and 12, will be analyzed using MMRM. The model will

Jazz Pharmaceuticals
 {Statistical Analysis Plan - Protocol #}JZP150-201-02

include randomized treatment group, corresponding score at Baseline, week (as a discrete factor), treatment by week interaction, baseline by week interaction, and randomization stratum as fixed effects, and week as a repeated effect. An unstructured variance-covariance matrix will be used to model the correlation among repeated measurements. The modeling detail and SAS code are similar to [Section 9.1.2](#).

9.2.6.5. Change in PGI-S and CGI-S from Baseline to Weeks 1, 4, and 8

PGI-S and CGI-S are described in [Section 9.2.1](#).

The change in participant and clinician-reported symptoms of PTSD as assessed by the PGI-S and CGI-S score from Baseline to Weeks 1, 4, and 8, will be analyzed using MMRM, separately for PGI-S, and CGI-S. The model will include randomized treatment group, corresponding score at Baseline, week (as a discrete factor), treatment by week interaction, baseline by week interaction, and randomization stratum as fixed effects, and week as a repeated effect. An unstructured variance-covariance matrix will be used to model the correlation among repeated measurements. The modeling detail and SAS code are similar to [Section 9.1.2](#).

9.2.6.6. Change in ISI and PSQI (with the PSQI-addendum) from Baseline to Week 12

The ISI is a 7-item participant-reported questionnaire assessing the nature, severity, and impact of insomnia in the past month. The ISI score is derived from the 7 questions that are rated on a 5-point scale from 0 to 4. Higher score indicates more severe sleep difficulties. The ISI score ranges from 0 to 28 and is assessed at Baseline and end of Weeks 1, 4, 8, and 12.

The PSQI (with the PSQI-addendum; PSQI-A) is a participant-report questionnaire evaluating sleep quality and sleep disturbance. The PSQI (with the PSQI-A) is comprised of 2 sections, (a) the core PSQI and (b) the PTSD specific addendum. The core PSQI consists of 19-items and the addendum is comprised of an additional 7 items that are commonly reported by adults with PTSD (e.g., hot flashes, memories or nightmares of the traumatic experience, and episodes of terror during sleep) ([Germain et al 2004](#)). The PSQI (with the PSQI-A) yields the following scores: 7 component scores, a global score, and a PSQI-A total score. The PSQI (with the PSQI-A) scores are calculated as outlined in [Appendix 1](#). The PSQI (with PSQI-A) is assessed at Baseline and end of Weeks 1, 4, 8, and 12. The PSQI (with PSQI-A) past week version is administered at end of Week 1 and the PSQI (with the PSQI-A) past month version is administered at Baseline and end of Weeks 4, 8, and 12.

The change in participant-reported sleep problems as measured by the ISI, PSQI (with the PSQI-A) from Baseline to Week 12 will be analyzed using an MMRM model, separately for ISI, PSQI global score and PSQI-A total score. The model will include randomized treatment group, corresponding score at Baseline, week (as a discrete factor), treatment by week interaction, baseline by week interaction, and randomization stratum as fixed effects, and week as a repeated effect. An unstructured variance-covariance matrix will be used to model the correlation among repeated measurements. The modeling detail and SAS code are similar to [Section 9.1.2](#).

The ISI, PSQI (with PSQI-A) data will also be summarized by time point. For the PSQI (with PSQI-A) descriptive statistics for the 7 component scores will be provided time point.

Jazz Pharmaceuticals
 {Statistical Analysis Plan - Protocol #}JZP150-201-02

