4.2.3. Other Secondary Endpoints

Other secondary efficacy endpoints include:

- CAPS-5 total score responder: Percent of participants with $\geq 30\%$ improvement on the CAPS-5 total score from Baseline to Week 12.
- CGI-C responder: Percent of participants who are very much or much improved on the CGI-C at Weeks 4 and 12.
- PGI-S responder: Percent of participants with ≥ 1 unit of improvement on the PGI-S from Baseline to Week 12.
- CAPS-5 total score change from Baseline to Week 4.

Jazz Pharmaceuticals
{Statistical Analysis Plan - Protocol #}JZP150-201-02

[figure not shown]
- Change in functional outcomes measured by the Brief Inventory of Psychosocial Functioning (B-IPF) and Sheehan Disability Scale (SDS) from Baseline to Week 12.
- Change in patient and clinician-reported symptoms of PTSD as assessed by the PTSD Checklist (PCL-5) from Baseline to Weeks 1, 4, 8, and 12.
- Change in patient and clinician-reported symptoms of PTSD as assessed by PGI-S and CGI-S from Baseline to Weeks 1, 4, and 8.
- Change in self-reported sleep problems as measured by the Insomnia Severity Index (ISI) and Pittsburgh Sleep Quality Index (PSQI; with the PSQI-addendum [PSQI-A]) from Baseline to Week 12.
- Change in PTSD symptom clusters (intrusive symptoms, avoidance symptoms, arousal/reactivity symptoms, and negative alterations in mood and cognition) as assessed by the change in the subscales of the CAPS-5 from Baseline to Weeks 4 and 12.
- Change in mood and anxiety as assessed by the change in Patient Health Questionnaire (PHQ-9) from Baseline to Weeks 1, 4, 12 and the change in the Structured Interview Guide for the Hamilton Anxiety Scale (SIGH-A) from Baseline to Weeks 4, 8, 12.
- Change in quality of life from Baseline to Week 12 as measured by the Recovering Quality of Life (ReQoL).

The safety endpoints of this study include:

- AEs
- Vital signs
- Physical examination (PE) [REDACTED]
- 12-lead electrocardiogram (ECG)
- Clinical laboratory tests (chemistry, hematology, urinalysis, [REDACTED]
[REDACTED])
- Columbia Suicide Severity Rating Scale (C-SSRS)
- Withdrawal scale (marijuana withdrawal checklist [MWC])

The PK/PD endpoints of this study include:

- Plasma concentration of Anandamide (AEA), JZP150 and its metabolites.

Jazz Pharmaceuticals
{Statistical Analysis Plan - Protocol #}JZP150-201-02

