5.4. Randomization and Blinding

All participants who sign the informed consent form (ICF) will receive a participant number. The participant number identifies the participant for all study procedures that occur throughout the study. This number is unique and once assigned cannot be reassigned to another study participant.

Treatment allocation/randomization for this study will occur centrally through the use of an interactive response technology (IRT). Following screening, eligible participants will be randomized (2:1:2) to one of three treatment arms: placebo, JZP150 0.3 mg QD, or JZP150 4 mg QD. Randomization will be stratified based on presence versus absence of use of a stable SSRI/SNRI at Screening. The sponsor, CRO, study investigators, clinical raters, and participants will be blinded to treatment assignment.

A double-blind approach will be used throughout the 12-week treatment period. During the study, the number of capsules taken each day will be the same for participants randomized to each treatment, and JZP150 and placebo capsules will look and feel identical.

The IRT will be programmed with blind-breaking instructions. In case of an emergency, the investigator has the sole responsibility for determining if unblinding of a participant's intervention assignment is warranted. Participant safety must always be the first consideration in making such a determination. If the investigator decides that unblinding is warranted, the investigator should make every effort to contact the sponsor prior to unblinding a participant's intervention assignment unless this could delay emergency treatment of the participant. If a participant's intervention assignment is unblinded, the sponsor must be notified within 24 hours after breaking the blind. The date and reason(s) that the blind was broken must be recorded in the source documentation and case report form, as applicable. The participant's treatment assignment may be unblinded for regulatory reporting purposes. Notification of the treatment assignment is only made known to those who require it for safety reporting and submission processes. All other individuals involved in the study, including the investigator (with the

Jazz Pharmaceuticals
 {Statistical Analysis Plan - Protocol #}JZP150-201-02

exception noted above), will remain blinded to treatment assignment. Participants for whom the blind is broken for this reason will not be withdrawn from the study.

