9.1.2. Main Analyses

The main analysis for the primary estimand will be conducted based on the Full Analysis Set 1, using treatment policy to address all ICEs. All CAPS-5 total score data collected through Week 12 regardless of ICEs will be used in the analysis, including the CAPS-5 total score data collected after an ICE. Using the main ICE of treatment discontinuation as the example, [Table 5](#) describes the detailed data mapping method for CAPS-5 total score scores following treatment discontinuation.

Table 5. Data mapping for CAPS-5 total score following treatment discontinuation for the main analyses.

Intercurrent event	CAPS-5 total score data mapping
If participant discontinues both study intervention and the study	CAPS-5 total score at E/D or any unscheduled visit will be mapped to Week 4 or Week 12, according to the windowing rule in Section 7.2.3 .
If participant discontinues study intervention prior to Week 4 but remains in the study	CAPS-5 total score at E/D visit, any unscheduled visit, the additional efficacy follow-up for Week 4, or efficacy follow-up visit for Week 12 will be mapped to Week 4 or Week 12, according to the windowing rule in Section 7.2.3 .
If participant discontinues study intervention between Week 4 and Week 12 but remains in the study	CAPS-5 total score at E/D visit, any unscheduled visit, or efficacy follow-up visit for Week 12 will be mapped to Week 12, according to the windowing rule in Section 7.2.3 .

A mixed-effect model with repeated measures (MMRM) will be used to analyze the primary efficacy endpoint, change in CAPS-5 total score from Baseline to Week 12.

$$dCAPS5TotalScore_{ij} = \alpha_i + \beta_1 * baseCAPS5TotalScore_i + \beta_2 * week_j + \beta_3 * treatment_i + \beta_4 * treatment_i * week_j + \beta_5 * baseCAPS5TotalScore_i * week_j + \beta_6 * stratum_i + \beta_7 * stratum_i * week_j + \varepsilon_{ij}$$

The model will include the CAPS-5 total score change from Baseline to Week 12 ($dCAPS5TotalScore_{ij}$) as the dependent variable; randomized treatment group ($treatment_i$), CAPS-5 total score at Baseline ($baseCAPS5TotalScore_i$), week (as a discrete factor, $week_j$), treatment group by week interaction ($treatment_i * week_j$), baseline by week interaction ($baseCAPS5TotalScore_i * week_j$), randomization stratum ($stratum_i$), and stratum by week interaction ($stratum_i * week_j$) as fixed effects, and week as a repeated effect.

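### The PGI-S responder comparison leaves out baseline PGI-S, and its reported difference and CI leave out the stratum as well: a modest loss of precision, not a bias

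*SAP*

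**What the plan says.** SAP 4.2.3 defines a PGI-S responder by at least one "unit of improvement on the PGI-S from Baseline to Week 12". SAP 9.2.1 gives the scale: "The responses to this participant-completed scale range from 1 (None) to 5 (Very severe").

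SAP 9.2.6.1 compares each dose with placebo "using the Cochran-Mantel-Haenszel (CMH) test stratified by randomization stratum". SAP 5.4 identifies the stratum: "Randomization will be stratified based on presence versus absence of use of a stable SSRI/SNRI at Screening". Severity is not a stratification factor. The text of 9.2.6.1 also promises a difference in proportions with a continuity-corrected Wilson/Newcombe interval. The example code for it is "TABLES TRT*RESPONDER1/RISKDIFF(CL=(WILSON(CORRECT" and so on, a treatment-by-response table with no stratum and no baseline term.

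The change-score models are built differently:
- The primary MMRM (SAP 9.1.2) has baseline CAPS-5 and a "baseline by week interaction".
- The CGI-S and PGI-S MMRMs (SAP 9.2.2) have "the CGI-S or PGI-S score at Baseline, and baseline by week interaction, as fixed effects".
- The B-IPF ANCOVA (SAP 9.2.6.3) has "randomized treatment group, randomization stratum, and B-IPF score at Baseline as covariates".
- The ReQoL-10 ANCOVA (SAP 9.2.6.9) also includes its baseline score.

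SAP 9.2.6 rules out sensitivity, subgroup and supplementary analyses for the secondary endpoints, and applies no multiplicity adjustment to them. A baseline-adjusted responder result is therefore planned nowhere.

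**The concern.** PGI-S response is likely to depend on where a participant starts. Someone at 1 cannot respond. Someone at 4 or 5 has more room to fall and more regression to the mean than someone at 3. If baseline predicts response, leaving it out has two effects. The response difference has a larger standard error than the same data allow. And, because randomization does not balance severity, any chance difference in baseline PGI-S between arms passes into the reported difference in proportions.

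The 0.3 mg comparison is the more exposed, with 38 expected completers against 75. A smaller inconsistency comes with it: the p-value respects the SSRI/SNRI stratum, while the estimate and CI beside it do not.

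The responder rates are descriptive companions to a key secondary endpoint in a study meant to guide later design and dose choice. The stake is how well they are estimated. No confirmatory claim rests on them.

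**Working it through.** **The plan's own figures.** No rate, effect size or power is given for any responder endpoint. The nearest figure is PGI-S change in SAP Table 4: effect size 0.50, power 86% (75 v 75) and 70% (38 v 75). A two-sample t-test at two-sided 0.05 has noncentrality 0.50/√(1/75 + 1/75) = 3.06 and 0.50/√(1/75 + 1/38) = 2.51. This gives 86.0% and 70.2%, so the stated figures reproduce.

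**Assumed inputs.** The documents give no PGI-S mean, SD or correlation. I took a latent normal score rounded to 1-5, with baseline mean 3.6, baseline SD 0.6-0.9, Week 12 SD 1.0 and placebo Week 12 mean 2.9. The baseline-to-Week 12 correlation ran from 0.2 to 0.7.

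**Does baseline predict response?** At baseline SD 0.75 and correlation 0.35, placebo response is about 43% from a baseline of 3, 68% from 4 and 86% from 5.

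**Variance explained.** With P_k the share of participants at baseline level k, p_k their response rate and p the overall rate,

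R² = 1 − Σ P_k p_k(1 − p_k) / [p(1 − p)].

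Adjusting multiplies the variance of the response difference by about 1 − R².

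| Correlation | SD 0.6 | SD 0.75 | SD 0.9 |
|---|---|---|---|
| 0.2 | 13% | 18% | 24% |
| 0.35 | 8% | 13% | 18% |
| 0.5 | 3-4% | 8% | 13% |
| 0.6 | 1% | 5% | 10% |
| 0.7 | 0.2% | 2% | 7% |

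Simulating whole trials (75 v 75, a 0.5 SD effect, correlations 0.2-0.5, 6,000 trials per setting) gave variance reductions of 3-24%, close to the first three rows.

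**Standard error, one case by hand.** A second parametrization has baseline SD 0.75, Week 12 SD 1.3 times that, mean improvement 0.8 and correlation 0.3. It gives p = 0.608 and R² = 0.153.
- Unadjusted SE = √[0.608 × 0.392 × (1/75 + 1/75)] = 8.0 percentage points.
- Adjusted SE = 8.0 × √(1 − 0.153) = 7.3 points.
- Equivalent gain in sample size = 1/(1 − 0.153) − 1 = 18%.

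At correlation 0.7 in the same setup, R² = 0.030, the SE goes from 7.8 to 7.7 points, and the gain is 3%.

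**Chance imbalance.** In the correlation 0.3 case, response rises by 0.240 per baseline point. The SD of the difference in mean baseline is 0.129 points (4 mg) or 0.157 (0.3 mg). A 1-SD imbalance therefore moves the unadjusted difference by 0.240 × 0.129 = 3.1 points, or 0.240 × 0.157 = 3.8 points, with no drug effect. Over correlations 0 to 0.7 the shift runs from 4.0 down to 1.3 points (4 mg) and from 4.9 down to 1.6 points (0.3 mg).

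**Power, 75 v 75.** At SD 0.75 and correlation 0.35 in the first setup:
- planned CMH: 61.2%
- CMH also stratified by baseline category (≤3, 4, 5): 65.2%
- standardized logistic estimate: 67.1%

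Across correlations 0.2-0.5 the logistic gain was about 2-11 points. In the second setup, the planned CMH against the baseline-stratified CMH gave 55% v 60% (correlation 0.3), 67% v 69% (0.5) and 81% v 80% (0.7).

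**Type I error.** The planned CMH rejected in 5.1% (75 v 75) and 4.6% (38 v 75) of null trials in the first setup, and in 4.8-5.4% in the second. The logistic estimate rejected in 4.9% and 5.5%. The Monte Carlo SE at 6,000 trials is √(0.05 × 0.95/6000) = 0.3 points.

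**The other two responders.** For the 30% CAPS-5 responder the variance reduction was only about 0-6%, because percent change already scales by baseline. For CGI-C, a change rating with no baseline value of its own, only baseline CGI-S could serve, and no gain was computed.

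**The case against.** The best defence is that nothing here is wrong, only less efficient. The CMH test stratified by the randomization factor holds its size, and a chance imbalance is sampling error that this size already covers. The responder endpoints sit outside the fixed sequence (SAP 7.4). Baseline PGI-S is already used in the PGI-S test that counts, the key secondary MMRM. The size of the gain rests on assumed inputs and nearly vanishes if baseline and Week 12 PGI-S correlate strongly. All of this stands, and it sets the severity.

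It does not remove the point. The score is already collected, the gain is positive when baseline predicts response, and no planned analysis supplies it.

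Four stronger readings are tempting, and the documents do not support them:
- **The responder result is biased or its test invalid.** It is not. The imbalance effect is an error within a given trial, not a systematic one.
- **The responder tests are the only efficacy comparisons without baseline.** The contingent Hodges-Lehmann estimates (SAP 9.1.3.3 and 9.2.6.3) have none either, although the p-values beside them come from models with ranked baseline.
- **All three responder endpoints lose materially.** The case is made for PGI-S only.
- **Adjustment would make the responder and MMRM results agree.** They also differ through dichotomization, the handling of missing data, and the MMRM's use of earlier visits.

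**Conclusion.** The point holds at low severity for PGI-S response. The planned comparison forgoes precision that is available at almost no cost. The variance of the response difference could fall by about 3-24% at baseline-to-Week 12 correlations of 0.2-0.5, and by about 0-10% at 0.6-0.7. A 1-SD chance baseline imbalance can move the reported difference by roughly 1 to 5 percentage points, depending on the correlation and the dose. These figures rest on an assumed baseline mean, SD and correlation for PGI-S. The structural facts do not: there is no baseline term in the test, and neither baseline nor stratum in the code for the difference and CI. The primary and key secondary conclusions are unaffected.

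**What to change.** In SAP 9.2.6.1, for PGI-S response and for each dose v placebo, specify a logistic model with treatment, SSRI/SNRI stratum and baseline PGI-S. Report the standardized (marginal) difference in proportions with a robust or delta-method 95% CI and p-value. The summary stays a difference in proportions, and the stratum enters the estimate and CI as well as the test. State in advance when cells are too sparse for the model, and fall back to the stratified CMH in that case.

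If a CMH test is preferred throughout, add baseline PGI-S category (≤3, 4, 5) as a second stratification factor. In the example above this recovers (65.2 − 61.2)/(67.1 − 61.2) = 68% of the power gain.

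Using the same model for CAPS-5 response (baseline CAPS-5) and CGI-C response (baseline CGI-S) is optional, with little or unquantified benefit.

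The cost is SAP wording and a few lines of code, with no new data. A model-based estimate replaces the simple table. Its small-sample behaviour is slightly less certain in the 0.3 mg comparison (about 38 v 75), where null rejection was 5.5% against 4.6% for the planned test.
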